8.3 ADVERSE EVENTS AND SERIOUS ADVERSE EVENTS

8.3.1 DEFINITION OF ADVERSE EVENTS (AE)

The FDA definition of an Adverse event is any untoward medical occurrence associated with the use of an intervention in humans, whether or not considered intervention-related (21 CFR 312.32 (a)). An AE can be either (a) a new occurrence or (b) an existing process (including the disease under study) that increases significantly in intensity or frequency. The medical product may be a drug or a device, being used either prior to or after regulatory approval.

8.3.2 DEFINITION OF SERIOUS ADVERSE EVENTS (SAE)

An AE is **serious** when the patient outcome is one or more of the following:

- Death. Applies to the event that is the primary cause of death
- Life-threatening, meaning that the patient was at immediate or substantial risk of death from the event at the time that the event occurred. It does not include an event which hypothetically might have caused death if it occurred in a more severe form.
- Hospitalization, initial or prolonged, meaning that a hospital admission and/or prolongation of a hospital stay was required for the treatment of the AE, or occurred as a consequence of the event. It does not include a pre-planned elective hospital admission for treatment or diagnostic procedures, or, in general, a hospital admission of less than 24 hours duration.
- Disability or incapacity that substantially disrupts the patient's ability to carry out normal life functions and is persistent or significant.
- Congenital anomaly or birth defect.
- Important medical event that, although not immediately life-threatening, requires intervention in order to prevent one of the other serious outcomes listed above. Examples of such events are allergic bronchospasm requiring intensive treatment in an emergency room or at home; blood dyscrasias or convulsions that do not result in hospitalization; or the development of drug dependency or drug misuse.

8.3.3 CLASSIFICATION OF AN ADVERSE EVENT

8.3.3.1 SEVERITY OF EVENT

For adverse events (AEs) not included in the protocol defined grading system, the following guidelines will be used to describe severity.

- **Mild** – Events require minimal or no treatment and do not interfere with the participant's daily activities.
- **Moderate** – Events result in a low level of inconvenience or concern with the therapeutic measures. Moderate events may cause some interference with functioning.
- **Severe** – Events interrupt a participant's usual daily activity and may require systemic drug therapy or other treatment. Severe events are usually potentially life-threatening or incapacitating. Of note, the term "severe" does not necessarily equate to "serious".

8.3.3.2 RELATIONSHIP TO STUDY INTERVENTION

All adverse events (AEs) must have their relationship to study intervention assessed by the clinician who examines and evaluates the participant based on temporal relationship and his/her clinical judgment. The degree of certainty about causality will be graded using the categories below. In a clinical trial, the study product must always be suspect.

- **Related** – The AE is known to occur with the study intervention, there is a reasonable possibility that the study intervention caused the AE, or there is a temporal relationship between the study intervention and event. Reasonable possibility means that there is evidence to suggest a causal relationship between the study intervention and the AE.
- **Not Related** – There is not a reasonable possibility that the administration of the study intervention caused the event, there is no temporal relationship between the study intervention and event onset, or an alternate etiology has been established.

8.3.3.3 EXPECTEDNESS

[name], study Principal Investigator (PI) will be responsible for determining whether an adverse event (AE) is expected or unexpected. An AE will be considered unexpected if the nature, severity, or frequency of the event is not consistent with the risk information previously described in the risk section for the study intervention.

8.3.4 TIME PERIOD AND FREQUENCY FOR EVENT ASSESSMENT AND FOLLOW-UP

The occurrence of an adverse event (AE) or serious adverse event (SAE) may come to the attention of study personnel during hospitalization or post-discharge follow-up data-collection phone calls.

All AEs including local and systemic reactions not meeting the criteria for SAEs will be captured on the appropriate case report form (CRF). Information to be collected includes event description, time of onset, clinician's assessment of severity, relationship to study product (assessed only by those with the training and authority to make a diagnosis), and time of resolution/stabilization of the event. All AEs occurring while on study must be documented appropriately regardless of relationship. All AEs will be followed to adequate resolution.

Any medical condition that is present at the time that the participant is screened will be considered as baseline and not reported as an AE. However, if the study participant's condition deteriorates at any time during the study, it will be recorded as an AE.

Changes in the severity of an AE will be documented to allow an assessment of the duration of the event at each level of severity to be performed. AEs characterized as intermittent require documentation of onset and duration of each episode.

A study coordinator will record all reportable events with start dates occurring any time after informed consent is obtained until 7 (for non-serious AEs) or 30 days (for SAEs) after the last day of study participation. At each study visit, the investigator will inquire about the occurrence of AE/SAEs since the last visit. Events will be followed for outcome information until resolution or stabilization.

Precautions and responses to possible specific adverse events:

Infection: The perineural catheters will be inserted under sterile conditions and affixed using liquid adhesive and a sterile occlusive chlorohexidine-impregnated dressing. Phone calls to participants will include questions regarding signs and symptoms of catheter site infection. Should a catheter site become suspicious for infection, the site will be evaluated by a physician investigator. If indicated, the

catheter will be removed, the catheter tip cultured, and the subject placed on the appropriate antibiotics.

Bleeding: There is the risk of bleeding since the needle and catheter will be inserted through the skin into muscle. If this was to happen, we would hold pressure until the bleeding stopped.

Catheter dislodgement. There is a risk of the catheter being accidentally and prematurely dislodged. The RELAY has small integrated anchors that theoretically decrease dislodgement (removal of the catheter is achieved by simply rotating the catheter which releases the anchors); liquid adhesive will be applied; a sterile occlusive dressing will cover the catheter entry site. Should a catheter be accidentally dislodged, participants have the option of returning to the center to have the catheter replaced as soon as possible. Of note, accidental catheter dislodgement has never been reported to cause injury—just a cessation of the perineural local anesthetic infusion.

Lead migration. The lead tip could migrate while the catheter/lead itself remains *in situ*. This could result in a decrease in analgesia. Should a catheter/lead migrate, participants have the option of returning to the center to have the catheter replaced as soon as possible.

Pain. Although we use local anesthetic to anesthetize the skin and muscle through which the implanting needle travels, participants may experience discomfort or pain during catheter and lead implantation as well as postoperative neurostimulation. If this occurs, we will administer intravenous fentanyl as is standard practice when administering peripheral nerve blocks. If the pain occurs postoperatively, participants will attempt to achieve pain relief by increasing amplitude of stimulation with the Gate Keeper app. participants in the training run-in period with a continuous peripheral nerve block, will use their pump's integrated bolus button to administer additional local anesthetic when needed if pain persists. If pain relief is not achieved and pain remains (NRS ≥ 4), participants are instructed to take prescribed opioids q4h. Note: Not all surgeons at UC San Diego use continuous peripheral nerve blocks; and those who do use them do so for some participants, but not others (depending on various surgical factors or simply their opinion of the technique).

Nerve injury (very low risk). The risk of a nerve injury with a local anesthetic-based peripheral nerve block is approximately 1 out of 10,000. No known nerve injuries have occurred with ultrasound-guided percutaneous neuromodulation, although it is theoretically possible. If a nerve injury was to occur, the participant would be referred to neurology for evaluation and management. The investigators would follow.

Confidentiality. The risks to confidentiality are the release of names/ telephone numbers/ demographic data (e.g. weight, age, height), which will be minimized by the use of password-protected computers and case report forms that will be stored in locked offices.

8.3.5 ADVERSE EVENT REPORTING

A member of the study staff shall complete a summary report or log of all AEs and submit to the UCSD Office of IRB Administration at the time of study annual renewal or closeout.

8.3.6 SERIOUS ADVERSE EVENT REPORTING

SAEs must be reported within 24 hours of discovery to Gate Science via a completed SAE form. The study investigator shall submit all SAEs to the UCSD Office of IRB Administration as soon as possible, but no later than 10 working days after the investigator first learns of the effect.

8.3.7 REPORTING EVENTS TO PARTICIPANTS

In the event of an SAE determined to be related to study procedure, participants will be informed after IRB review of the event. Upon IRB acknowledgement and study team fulfillment of any protocol changes, participants will be informed via a consent form addendum or a new version of the consent form. Participants will be given the choice to withdraw from the study or sign the new consent and continue.

8.3.8 EVENTS OF SPECIAL INTEREST

Not applicable.

8.3.9 REPORTING OF PREGNANCY

Conception following the surgical procedure is not considered an AE for this study: there is no prohibition against pregnancy with peripheral nerve stimulation (it is far preferred over systemic opioid consumption).

8.4 UNANTICIPATED PROBLEMS

8.4.1 DEFINITION OF UNANTICIPATED PROBLEMS (UP)

The Office for Human Research Protections (OHRP) considers unanticipated problems (UP) involving risks to participants or others to include, in general, any incident, experience, or outcome that meets all of the following criteria:

- Unexpected in terms of nature, severity, or frequency given (a) the research procedures that are described in the protocol-related documents, such as the Institutional Review Board (IRB)-approved research protocol and informed consent document; and (b) the characteristics of the participant population being studied;
- Related or possibly related to participation in the research (“possibly related” means there is a reasonable possibility that the incident, experience, or outcome may have been caused by the procedures involved in the research); and
- Suggests that the research places participants or others at a greater risk of harm (including physical, psychological, economic, or social harm) than was previously known or recognized.

8.4.2 UNANTICIPATED PROBLEM REPORTING

The investigator will report UPs to Gate Science and to UCSD Office of IRB Administration. The UP report will include the following information:

- Protocol identifying information: protocol title and number, PI's name, and the IRB project number;
- A detailed description of the event, incident, experience, or outcome;
- An explanation of the basis for determining that the event, incident, experience, or outcome represents an UP;
- A description of any changes to the protocol or other corrective actions that have been taken or are proposed in response to the UP.

To satisfy the requirement for prompt reporting, UPs will be reported using the following timeline:

- UPs that are serious adverse events (SAEs) will be reported to the IRB within 10 days of the investigator becoming aware of the event.

- Any other UP will be reported to the IRB within 30 days of the investigator becoming aware of the problem.
- All unanticipated events and adverse events will be reported to the supervising IRB (University of California San Diego).

8.4.3 REPORTING UNANTICIPATED PROBLEMS TO PARTICIPANTS

In the event of a UP determined to be related to study procedure, participants will be informed after IRB review of the event. Upon IRB acknowledgement and study team fulfillment of any protocol changes, participants will be informed via a consent form addendum or a new version of the consent form. Participants will be given the choice to withdraw from the study or sign the new consent and continue.

9 STATISTICAL CONSIDERATIONS

9.1 STATISTICAL HYPOTHESES

Hypothesis 1: Neuromodulation with the RELAY device will decrease **average pain intensity** for Days 1-7 following foot and shoulder surgery currently treated with a single-injection peripheral nerve block (as measured with the NRS within the BPI).

Hypothesis 2: Neuromodulation with the RELAY device will decrease **opioid consumption** within the week following foot and shoulder surgery currently treated with a single-injection peripheral nerve block (measured in oxycodone equivalents), as measured both with daily and cumulative opioid consumption within the first postoperative week).

Hypothesis 3: **Physical and emotional functioning** as measured with the Interference Subscale of the BPI. Neuromodulation with the RELAY device will decrease pain's **interference** in physical and emotional **functioning** within the week following foot and shoulder surgery currently treated with a single-injection peripheral nerve block.

9.2 SAMPLE SIZE DETERMINATION

The sample size estimation is centered around the hypothesis that neuromodulation lowers the severity of pain the week after surgery. To this end, the primary outcome measure is the median "average" daily pain intensity for Days 1-7 as measured with the NRS within the BPI. This outcome measure was used by the authors previously for a similar study treating the same patient population with a different percutaneous peripheral nerve stimulation pulse generator and lead, and we therefore will use the resulting mean (SD) from each treatment group to power the present pilot study [Ilfeld et al. Anesthesiology 2021; 135: 95-110]. Specifically, the treated and sham groups reported a mean (SD) of 1.1 (1.1) and 3.1 (1.7), respectively. Assuming a standard deviation of 2.05, a sample size of 20 participants per group provides 85.2% power to detect a group difference of 2 points. With an additional 10 participants allowed to replace drop-outs in the randomized portion, a total of up to 70 participants may be enrolled in this study combining the run-in and randomized stages.

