9.4.2 ANALYSIS OF THE PRIMARY EFFICACY ENDPOINT(S)

The primary analytic approach will be an unadjusted two-sample Mann-Whitney U test of the median value of each participant's average daily NRS for Days 1, 2, 3, 4, and 7 (data is not collected on Days 5 and 6). If any key variables are imbalanced at baseline, a linear regression model, or appropriate generalized linear model, adjusting for those variables will be applied. The p-value and 95% confidence interval associated with the estimated group difference in average daily NRS will be provided. $P<0.05$ will be considered statistically significant for the primary outcomes.

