9.4.6 PLANNED INTERIM ANALYSES

A futility analysis will be performed once 20 participants have been randomized and data through post-operative Day 7 are available. The following two criteria must be achieved to move forward: 1) RELAY deployment success in the lead/catheter insertion of $\geq 85\%$ in RELAY participants, and 2) a conditional power (Cp) of $\geq 30\%$ for the primary efficacy endpoint. Of note, a standardized effect size of 0.49 would not meet criteria to continue. There will be no stopping for early efficacy.

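### Section 9.2 takes its SDs (1.1 and 1.7) from a cited study but assumes 2.05, which equals their pooled variance; the pooled SD is 1.43, so 85.2% is not the power that source implies

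*Combined protocol and SAP*

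**What the plan says.** Section 9.2 rests the sample size on an earlier trial by the same group, which used another stimulator and lead. It states: "we therefore will use the resulting mean (SD) from each treatment group to power the present pilot study". The figures follow: "the treated and sham groups reported a mean (SD) of 1.1 (1.1) and 3.1 (1.7), respectively". The next sentence reads "Assuming a standard deviation of 2.05, a sample size of 20 participants per group provides 85.2% power" for a difference of 2 points. The section does not say where 2.05 comes from, and it names neither a test nor an alpha for the power.

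Two other sections bear on what the power figure means. In 9.4.2, "The primary analytic approach will be an unadjusted two-sample Mann-Whitney U test". In 9.4.6 a futility look takes place after 20 participants, with the words "The following two criteria must be achieved to move forward". One criterion is conditional power of at least 30%. The section adds: "Of note, a standardized effect size of 0.49 would not meet criteria to continue".

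**The concern.** The 2-point difference is the difference of the cited means, 3.1 - 1.1. The SD should come from the same source, because the text says so, yet 2.05 is larger than both cited SDs. It also equals, to the second decimal, the average of the two squared SDs. That pattern suggests a variance was used where an SD was meant.

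Section 9.2 is the only justification for the number randomized, and a reader cannot tell whether 2.05 is a deliberate margin or a slip. The answer moves the power for 2 points from about 85% to about 99%. The trial's stated purpose is to prepare a larger one. Because sample size scales with variance, carrying 2.05 forward in place of 1.43 would roughly double the planned size (2.05² = 4.20 against 2.05).

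**Working it through.** **Inputs.** From 9.2: SDs 1.1 and 1.7, means 1.1 and 3.1, 20 per group, difference 2, assumed SD 2.05, stated power 85.2%. Alpha is two-sided 0.05 from 9.4.3; the synopsis's one-sided 0.025 gives the same power here.

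**1. Reproduce the plan's figure.** For a two-sample t-test with 38 degrees of freedom, the noncentrality is (difference/SD) × √(n/2) = (2/2.05) × √10 = 3.085. Noncentral-t power is 85.23%, which matches 85.2%. A one-sided 0.05 test would give 91.7%, which does not.

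**2. Pool the cited SDs.** With equal weights:
- pooled variance = (1.1² + 1.7²)/2 = (1.21 + 2.89)/2 = 2.05
- pooled SD = √2.05 = 1.43

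The documents do not give the cited arm sizes, so equal weighting is an assumption. With twice as many sham as treated participants, the SD is √[(1.21 + 2 × 2.89)/3] = 1.53. With the reverse ratio it is √[(2 × 1.21 + 2.89)/3] = 1.33. No weighting can exceed 1.7.

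**3. Power at the alternatives.** t-test, 20 per group, two-sided 0.05, before any futility stop:

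| SD | Difference | Power |
|---|---|---|
| 2.05 | 2 | 85.2% |
| 1.7 (larger cited SD in both arms) | 2 | 95.2% |
| 1.53 | 2 | 98.1% |
| 1.43 | 2 | 99.0% |
| 1.33 | 2 | 99.6% |
| 1.43 | 1.4 | 85.4% |

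At SD 1.43, 85.2% power for 2 points needs about 10.3 per group.

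**4. Effect of the futility stop.** Section 9.4.6 does not say how conditional power is computed, so I used its remark about 0.49 to identify the rule. With 10 per group at half the information, the interim Z at d = 0.49 is 0.49 × √5 = 1.096.
- Current trend: Φ[(1.096 × √2 - 1.96)/√0.5] = 0.281, just below 0.30. The threshold of 0.30 is reached at d = 0.5025.
- Design alternative: the same d gives 0.693 (SD 2.05) or 0.926 (SD 1.43), and the trial would continue.

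The remark therefore fits a current-trend rule and not a design-alternative rule. I simulated 200,000 trials per case with normal data, 10 then 20 per arm, and a binding stop at d below 0.5025. Simulation error is at most 0.1 percentage point.

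| SDs, difference | t-test without / with stop | Mann-Whitney without / with stop |
|---|---|---|
| 2.05, 2 points | 85.3% / 78.5% | 83.2% / 76.9% |
| 1.1 and 1.7, 2 points | 99.0% / 97.1% | 98.5% / 96.6% |
| 1.43, 1.4 points | 85.4% / 78.7% | 83.3% / 77.1% |

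The deployment-success criterion was not modelled. Mann-Whitney power at SD 2.05 depends on the distribution. Scores rounded and clipped to 0-10, tuned to the same means and SD, give about 93% before the stop and 81% after it.

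**The case against.** The strongest defence is that 9.2 openly assumes 2.05 and that 85.2% is correct for it, so this is an unexplained input and not a miscalculation. That is fair as far as it goes: the arithmetic after the SD is right, and a variance-for-SD slip is an inference. But the text says the cited study's SDs will be used, and the value used cannot come from them as an SD.

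A wider SD might also be prudent. The cited study used a different device. Section 2.2 reports that the sponsor's own RELAY pilot enrolled 29 of 63 planned participants before an interim analysis judged a demonstration of efficacy unlikely. A bare 99% would look too favourable against that record. This stands as a reason to keep a conservative SD and say so; it does not supply the missing explanation.

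The practical effect is small, and that stands too. On the cited inputs the discrepancy is conservative, 2.05 appears only in 9.2, and the futility rule does not use it.

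Finally, the futility and Mann-Whitney figures go beyond the SD question, and the 1.4-point case is only an illustration with no source in the plan. The with-stop figures rest on a rule the plan does not name, and the clipped-score model piles about 68% of treated participants at zero. They show what a restated power would mean; the finding does not depend on them.

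**Conclusion.** The point holds with high confidence. The assumed SD equals the equal-weight pooled variance of the cited SDs, and the stated 85.2% is not the power its stated source implies. On that source, two-sided 0.05 t-test power for 2 points with 20 per group is 99.0% (98.1% to 99.6% for cited-arm ratios from 1:2 to 2:1), and 95.2% even if the larger SD applied to both arms. These figures rest on normal-theory t-test power before the futility stop. Sample size, type I error and enrolment are unaffected. It should be fixed because the only power statement contradicts its own source and may be carried into the next trial.

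**What to change.** In 9.2, do one of two things:
- state that the cited SDs pool to 1.43 (equal weights assumed), giving about 99% power for 2 points with 20 per group, or about 85% for 1.4 points; or
- keep 2.05, label it a deliberately conservative planning SD not taken from the cited study, give the reason, and retain 85.2%.

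In either case, say that the power is for a two-sided 0.05 t-test before the futility stop in 9.4.6. Then give the power with the stop and its assumptions. If it is binding and on current-trend conditional power with normal data, t-test power is about 79% at SD 2.05 and 97% at the cited SDs; Mann-Whitney power is about 77% and 97%. Any Mann-Whitney power should name the distribution assumed.

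The correction of the SD takes one or two sentences. The with-stop statement adds another and needs a short simulation to confirm it. No patients, procedures or trial analyses are added.

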9.4 STATISTICAL ANALYSES

9.4.1 GENERAL APPROACH

Baseline characteristics of the randomized groups will be summarized with means, standard deviations, and quartiles. Balance between groups will be assessed following the approach described by Schober (2018). Specifically, standardized differences will be calculated using Cohen's d whereby the difference in means or proportions is divided by the pooled standard deviation estimates. Any key variables (age, sex, height, weight, BMI, and surgical procedure) with an absolute standardized difference greater than $1.96 \times \sqrt{2/n} = 0.716$, where $n = 15$ is the target sample size per group (Austin (2009)), will be noted and included in a sensitivity analysis with a generalized linear model (e.g. linear regression for pain severity NRS or logistic regression for incidence rates) to obtain an estimate of the treatment effect adjusted for the imbalanced covariate(s). If key model assumptions are violated (i.e. homoscedasticity or Gaussian distribution for linear models), data transformations and/or alternative generalized linear models will be applied as appropriate. Missing data is expected to be negligible. In the event of unexpected missing data, multiple imputation by chained equations (Stef van Buuren, Karin Groothuis-Oudshoorn (2011). mice: Multivariate Imputation by Chained Equations in R. *Journal of Statistical Software*, 45(3), 1-67) will be applied to obtain estimates of treatment effects under the assumption of missing at random. The imputation model will exhaustively consider all measured baseline covariates and longitudinal observations to maximize the likelihood that the missing at random assumption is met.

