9.4.3 ANALYSIS OF THE SECONDARY ENDPOINT(S)

Continuous endpoints will be analyzed with the same approach as the primary endpoint. Binary endpoints will be analyzed with Fisher's Exact test for two proportions, or logistic regression in the event of imbalance on key baseline variables. Ordinal endpoints will be analyzed with the Armitage trend test, or cumulative link regression model as warranted. We will test key secondary outcomes using a serial gatekeeping procedure. Nominal 95% confidence intervals will be provided for secondary analyses.

Study-wide Type I error control. We will use a serial gatekeeping procedure to control the study-wide type I error at 0.05 [Mascha EJ, Turan A: Joint hypothesis testing and gatekeeping procedures for studies with multiple endpoints. *Anesth Analg* 2012; 114: 1304-17]. For this procedure we therefore have prioritized (*a priori*) the study outcomes (**Table below**). Analysis will proceed in that order, and testing will proceed through each "gate" to the next set if and only if the outcome in the current set reaches significance. The significance level for each set will be 0.05 times a cumulative penalty for non-significant results in previous sets (i.e., a "rejection gain factor" equal to the cumulative product of the proportion of significant tests across the preceding sets). We will use the corresponding 2-tailed alpha level of 0.05 for the gatekeeping, as all sets involve 2-tailed tests. Treatment effects will also be assessed at individual time points regardless of preceding gatekeeping results, and no other adjustments will be made for testing multiplicity.

Serial gatekeeping procedure

Sets	Time frame	Required to pass to next set
------	------------	------------------------------

1: Pain intensity (median of 5 daily “average” NRS)	1 st week	Significance on this outcome
2: Cumulative opioid use (oxycodone equivalents)	1 st week	Significance on this outcome
3: BPI interference subscale	Postop Day 3	Significance on this outcome
4: Pain intensity (median of 5 daily “worst” NRS)	1 st week	Significance on this outcome
5: BPI interference subscale	Postop Day 7	Significance on this outcome
6: Cumulative awakenings due to pain	1 st week	Significance on this outcome
7: Pain intensity (“average” NRS)	Postop Day 7	Significance on this outcome
8: Pain intensity (“worst” NRS)	Postop Day 7	Significance on this outcome
9: Opioid use (oxycodone equivalents)	Postop Day 7	Significance on this outcome

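### The 85.2% power in section 9.2 belongs to a fixed-sample t-test; for the planned Mann-Whitney test with the conditional-power stop it is about 77% on the same assumptions, if conditional power uses the observed trend

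*Combined protocol and SAP*

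**What the plan says.** Section 9.2 states that "a sample size of 20 participants per group provides 85.2% power to detect a group difference of 2 points", assuming an SD of 2.05. It names no test and does not mention the interim look. The same paragraph cites a prior study of another stimulator, whose treated and sham groups "reported a mean (SD) of 1.1 (1.1) and 3.1 (1.7), respectively".

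Section 9.4.2 sets the primary analysis: "The primary analytic approach will be an unadjusted two-sample Mann-Whitney U test", applied to each participant's median of five daily scores. On the significance level, 9.4.3 says: "We will use the corresponding 2-tailed alpha level of 0.05 for the gatekeeping". The synopsis words it as one-sided 0.025, which gives the same power.

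Section 9.4.6 plans a futility look once 20 participants are randomised and have Day 7 data. Its wording is binding: "The following two criteria must be achieved to move forward". The criteria are deployment success of at least 85% in the RELAY arm and conditional power of at least 30% for the primary endpoint. It adds: "Of note, a standardized effect size of 0.49 would not meet criteria to continue" and "There will be no stopping for early efficacy". It does not give the effect under which conditional power is computed, or the interim statistic.

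**The concern.** A reader of 9.2 will take 85% as the chance of a significant primary result if the 2-point effect is real. Two features of the plan are missing from that figure. The rank test differs from the t-test in power. A futility stop with no matching early efficacy stop can only remove successes, so it cannot raise power.

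The size of the loss depends on the effect assumed in conditional power, and the plan leaves the reader to infer that from one remark. The same gap affects conduct: different readings of the 30% rule would stop different trials on the same data.

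**Working it through.** **Inputs.** Difference 2 points, SD 2.05, 20 per group (9.2); two-sided 0.05 (9.4.3); Mann-Whitney (9.4.2); look at 20 of 40 participants and a 30% threshold (9.4.6). I take 10 per arm at the look, so the information fraction is t = 0.5.

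**1. Reproduce the stated figure.** d = 2/2.05 = 0.976. Noncentrality = 0.976 × √(20/2) = 3.085, with 38 df. Power of the two-sided 0.05 t-test = 85.23%. The stated 85.2% is reproduced exactly, as a fixed-sample t-test.

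**2. Which conditional power does the 0.49 remark fit?** At d = 0.49, interim z = 0.49 × √(10/2) = 1.096 and B = z√t = 0.775. Conditional power = Φ[(B + θ(1 − t) − 1.960)/√(1 − t)], where θ is the assumed drift. The 30% boundary is where B + θ(1 − t) = 1.960 − 0.524 × 0.707 = 1.589. P(stop) is exact at a true d of 0.976 (noncentral t, 18 df).

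| Assumed effect | θ | Cond. power at d = 0.49 | 30% boundary | P(stop) |
|---|---|---|---|---|
| Observed trend | B/t = 1.549 | 28.1% | z = 1.124, d = 0.503 | 14.6% |
| Design effect | 3.085 | 69.3% | z = 0.066, d = 0.029 | 1.7% |
| Null effect | 0 | 4.7% | z = 2.247, d = 1.005 | 51.3% |

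The design-effect reading contradicts the remark, because 0.49 would continue. The null-effect reading agrees that 0.49 stops, but its boundary is about twice that value. Only the observed trend puts the boundary just above 0.49 (0.503 × 2.05 = 1.03 points).

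**3. Power of the planned design.** Simulation of 200,000 trials with normal scores, means 1.1 and 3.1, SD 2.05, 10 then 20 per arm, two-sided 0.05:

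| Design | Power |
|---|---|
| t-test, no look | 85.3% |
| Mann-Whitney, no look | 83.3% |
| Mann-Whitney, observed-trend stop, mean-based look | 76.9% |
| Mann-Whitney, observed-trend stop, rank-based look | 76.0% |
| Mann-Whitney, design-effect stop | 83.0% |
| Mann-Whitney, null-effect stop | 47.3% |

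A continuity-corrected rank look gives about 75%. A separate run gave 83.2% without the look and 76.7% with the mean-based observed-trend look. The phrase 'standardized effect size', and the Cohen's d of 9.4.1 ("whereby the difference in means or proportions is divided by the pooled standard deviation estimates"), suggest a mean-based look but do not settle it.

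**4. Where the loss arises.** The change of test costs about 2 points and the stop about 6. Of the trials stopped under the observed trend, 43% would have been significant at 40 participants: 0.434 × 14.6% = 6.3% of all trials.

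**5. Sensitivity.**
- SDs of 1.1 and 1.7, normal scores: Mann-Whitney 98.5% without the look. With the observed-trend stop: 96.7% (mean-based), 96.0% (rank-based), about 95% (rank-based, continuity-corrected).
- No true difference: two-sided rejection 4.9% without the stop and 1.9% with it.
- Deployment criterion: with 10 active participants at the look, 9 of 10 (90%) passes and 8 of 10 (80%) fails. The documents give no true success rate. At assumed rates of 90%, 95% and 98%, the chance of passing is 74%, 91% and 98%. None of the power figures above includes this.

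**The case against.** The strongest objection concerns the 77% itself. Normal scores with a mean of 1.1 and an SD of 2.05 put about 30% of the active arm below zero, on a scale that runs from 0 to 10. Shapes confined to the scale, all of them assumed, gave power with the observed-trend stop from about 73% to 91%. Normal scores rounded and cut off at 0 and 10 gave about 74-75%. A rounded beta shape with the same means and SD gave about 82% with a mean-based look and about 92% with a rank-based one, and there Mann-Whitney without the look (96%) exceeded the t-test figure. This stands: 77% is the counterpart of 85.2% under the plan's own simple model, not a forecast, and the interim statistic can matter more than it does on normal data.

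It also stands that 85.2% is the reproducible basis for 20 per group and should not be deleted, and that no figure for the planned design should go into 9.2 until the sponsor confirms the conditional-power effect.

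Three other defences do not remove the point. The planning SD is larger than the cited ones, but a figure stated at SD 2.05 has to hold at SD 2.05. The study is a pilot, but it states formal power and claims study-wide error control. Type I error is not inflated, but that does not bear on power.

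**Conclusion.** The point holds as a mislabelled and incomplete power statement. Under normal scores, SD 2.05 and a 2-point difference, the planned Mann-Whitney test has about 83% power. Counting the 30% conditional-power stop, it has about 77% (75-77% by interim statistic) under the observed trend. The shortfall from 85.2% is about 8 points, mostly from the stop. The 77% rests on the observed-trend reading, which the 0.49 remark favours but 9.4.6 does not state. The design-effect reading would give about 83% and the null-effect reading about 47%.

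A reader might infer more than the documents support:
- That 85.2% is an arithmetic error. It is exact for the calculation behind it.
- That the trial is underpowered and needs more participants or a looser stop. At the cited SDs, power with the stop is about 95-97%, and the documents do not show which SD will apply.
- That 77% is a bound or the true power. It depends on score shape, which the documents do not give, and it leaves out the deployment criterion.
- That the look inflates type I error. It lowers it.

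**What to change.** 1. **Section 9.4.6.** State the effect under which conditional power is computed: the observed trend, with its boundary at d of about 0.50, if the sponsor confirms that this is what the 0.49 remark means. Name the interim statistic (mean-based or rank-based).

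2. **Section 9.2.** Keep 85.2%, labelled as the fixed-sample two-sided 0.05 t-test figure behind 20 per group. Then give the power of the planned design under the confirmed rule. If that is an observed-trend, mean-based look, the figure is about 77% for Mann-Whitney (normal data, SD 2.05, 2 points), against about 83% without the look.

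3. **Conditions to print with that figure.** It excludes the deployment criterion. It depends on score shape and interim statistic, and 0-10 scores at SD 2.05 can give lower or higher values. It is about 95-97% at the cited SDs of 1.1 and 1.7.

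Optionally, 9.4.6 could note that with 10 active participants at the look the 85% deployment criterion allows one failure.

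The cost is a few sentences and a less favourable stated power. Sample size, both criteria and data collection stay as they are.
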